4.2.3 Correction Phase Day 3 (Visit 4)

Subjects will arrive at the clinic in the morning after fasting for at least 8 hours prior to potassium sample collection.

- The clinic staff will solicit any adverse events, note any changes in concomitant medications, note if the subject has visited a doctor or emergency room since the last visit, examine the investigational product dosing boxes and sachets and make note of the time the doses were taken and any unused investigational products on the eCRF and source documents.
- Potassium values will be evaluated by i-STAT and the Central Laboratory.
- If the i-STAT potassium value is between 3.0 and 3.4 mmol/L inclusive, the subject should not take a study IP doses that day and return the next day to assess potassium.
- If the i-STAT potassium value is between 3.5 and 5.0 mmol/L, inclusive, the subject will enter the Maintenance Phase and complete the procedures detailed in Section 4.2.5.
- If the i-STAT potassium value is ≥ 5.1 mmol/L, the subject will receive an additional 24 hours of ZS 10 g TID and the following procedures will be performed:
 - The site will access the IVRS/IWRS and provide the 7-digit subject identification number. The system will assign the subject an investigational product kit.
 - Obtain vital signs (pulse rate and blood pressure) (Section 5.2.4).
 - An ECG will be performed (Section 5.2.3).

- The morning dose of ZS will be administered in the clinic as a suspension in water.
 - Subjects will then be sent home with 2 doses of study drug and instructions on how to take ZS. They will be requested to fill out a dosing schedule card indicating when they took ZS.
 - Subjects will return to the clinic the following morning and bring the used investigational product boxes and sachets and dosing schedule card with them.
- See section 7.2 regarding how to handle patients with potassium < 3.5 mmol/L.

4.2.4 Correction Phase Day 4 (Visit 5) (Visit 5 is only for patients who needed 72 hour correction phase.)

[figure not shown]
Subjects will arrive at the clinic in the morning after fasting for at least 8 hours prior to potassium sample collection.

- The clinic staff will solicit any adverse events, note any changes in concomitant medications, note if the subject has visited a doctor or emergency room since the last visit, examine the investigational product dosing boxes and sachets and make note of the time the doses were taken and any unused investigational products on the eCRF and source documents.
- Potassium values will be evaluated by i-STAT and the Central Laboratory.
- If the i-STAT potassium value is between 3.5 and 5.0 mmol/L, inclusive, the subject will enter the Maintenance Phase and complete the procedures detailed in Section 4.2.5.
- If the i-STAT potassium value is < 3.5 or ≥ 5.1 mmol/L following 72 hours of dosing with ZS 10 g TID, the following procedures will be performed:
 - Collect blood samples for assessment of hematology and clinical chemistry.
 - Collect urine samples for assessment of urinalysis parameters.
 - Obtain vital signs (pulse rate and blood pressure) (Section 5.2.4).
 - An ECG will be performed (Section 5.2.3).
 - The site will access the IVRS/IWRS, provide the 7-digit subject identification number, and document that the subject did not qualify for the Maintenance Phase.
 - Subjects will then DISCONTINUE from the study, and receive standard of care at the discretion and the direction of his/her own physician. However, the subject will need to return to the clinic in the morning, fasting for at least 8

[figure not shown]
Clinical Study Protocol
Drug Substance ZS
Study Code D9482C00001
Version 5.0
Date 13 Sep 2018

hours prior to potassium sample collection, 7 (\pm 1) days later after the last administration of IP for an End of Study visit.

Figure 4 Flow chart based on the S-K level: Correction Phase

S-K: Serum potassium, QD: Once daily, TID: Three times daily
 *: Confirmation by an additional measurement after 10 minutes is required.

S-K: Serum potassium, QD: Once daily, TID: Three times daily
*: Confirmation by an additional measurement after 10 minutes is required.

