Correction Phase: If the subject is normokalemic (i-STAT [A portable blood analyser] potassium between 3.5 and 5.0 mmol/L, inclusive) on the morning of Correction Phase Study Day 2 after 3 doses of ZS 10 g, they will enter the Maintenance Phase. If the subject is not normokalemic, they will receive an additional 24 hours of ZS 10 g TID treatment (6 total doses). If the subject's i-STAT potassium value is between 3.5 and 5.0 mmol/L, inclusive, on the morning of Correction Phase Study Day 3, the subject will enter the Maintenance Phase. If the subject is not normokalemic, they will receive an additional 24 hours of ZS 10 g TID treatment (9 total doses). If the subject's i-STAT potassium value is between 3.5 and 5.0 mmol/L, inclusive, on the morning of Correction Phase Study Day 4, the subject will enter the Maintenance Phase. If the i-STAT potassium value is still < 3.5 mmol/L or ≥ 5.1 mmol/L on the morning of Correction Phase Study Day 4, after 72 hours of TID treatment, the subject will be withdrawn from the study and referred to their normal health care provider for standard of care treatment. Subjects withdrawn from the Correction Phase of the study will return to the clinic 7 (± 1) days after their last dose of ZS for an End of Study (EOS) visit.

Maintenance Phase: Patients will initially be dosed with ZS at a starting dose of 5g QD. Potassium (i-STAT and central laboratory) will be measured as indicated in the study schedule (Table 2). During the Maintenance Phase, the ZS dose may be increased up to 15 g QD or decreased down to 5g QOD (or 2.5 g QD) based on i-STAT potassium measurements as outlined in Section 7.2.

Throughout all phases of the study, most potassium values will be measured at fasting before taking ZS. Nothing should be taken by mouth except water, coffee or tea, with or without milk and/or sugar, and essential medications, for a minimum of 8 hours prior to the blood collection. Potassium level should be determined by both i-STAT and the Central Laboratory on all occasions. Treatment decisions (eg, dose titration, stopping rules) will be made based on i-STAT potassium values, as these provide clinical sites with a real-time measurement, according to dose modification rules as described in Section 7.2. Statistical analyses on the study data will in principle be based on S-K values as measured by the Central Laboratory.

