3.9 Discontinuation of investigational product

Patients may be discontinued from investigational product (IP) in the following situations:

- Patient decision. The patient is at any time free to discontinue treatment, without prejudice to further treatment
- Adverse Event
- Severe non-compliance with the Clinical Study Protocol
- Risk to patient as judged by investigator
- Pregnancy
- Require treatment with medications prohibited or contraindicated for use due to safety concerns with ZS
- Patient develops potassium values which meet the IP discontinuation criteria described in [Table 6](#) (confirmed by taking a second potassium measurement after a 10 ± 2 -minute interval, and both i-STAT values meet the study drug discontinuation rule). Patients discontinuing due to this criterion must immediately receive appropriate medical treatment to manage their hypo- or hyperkalemia.

Patient develops clinically significant cardiac condition (see below). The patient should immediately receive appropriate medical treatment and be discontinued from study drug.

- Serious cardiac arrhythmias (ventricular tachycardia or ventricular fibrillation, new atrial fibrillation or atrial flutter, new paroxysmal supraventricular tachycardia [other than sinus tachycardia], new 2nd or 3rd degree AV block or significant bradycardia [HR < 40 bpm])
- Acute heart failure
- Significant increase in PR interval (> 250 msec in the absence of pre-existing atrioventricular block) or widening of the QRS complex (>140 msec in the absence of pre-existing bundle branch block). If an ECG shows peaked T-wave, the serum potassium must be checked immediately and decide whether to continue the IP based on the criteria described in [Section 3.9](#).
- An absolute QTc >550msec, or an increase in QTc interval > 60msec from baseline to more than 500msec. All patients meeting the QTc>500ms criterion should immediately have potassium assessed by i-STAT and central lab, if not already done within 1 hour of the collection of the ECG

Patients who discontinue from study medication during the Correction Phase conduct Visit5 procedure soon after the discontinuation and conduct EOS Visit one week after last IP.

Patients who discontinue from study medication during the Maintenance Phase conduct Visit23 procedure soon after the discontinuation and conduct EOS Visit one week after last IP.

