4. STUDY PLAN AND TIMING OF PROCEDURES

Table 1 Study Plan for the Correction Phase

Study Visit	Visit 1	Visit 2 ⁷	Visit 3 ⁵	Visit 4 ⁵	Visit 5 ⁵	EOS ⁶
Correction Phase Day	Screening	Day 1 ⁷	Day 2 ⁵	Day 3 ⁵	Day 4 ⁵	Day 10 ⁶
Written informed consent	X					
Eligibility criteria		X				
Demographics	X					
Medical History		X				
SF-36 v2 questionnaire		X				
Physical exam including weight		X ⁸				X ⁸
Access IVRS/IWRS	X	X	X ⁹	X ⁹	X ⁹	
Study drug (IP) dispensation		X	X ⁹	X ⁹		
Study drug (IP) administration		X	X ⁹	X ⁹		
ECG		X	X ⁹	X ⁹	X ⁹	X
Vital signs		X		X ⁹	X ⁹	X
Concomitant medications		X	X	X	X	X
Adverse events		X ¹⁰	X	X	X	X
Potassium ¹		X ²	X ^{3,11}	X ¹¹	X ¹²	X ¹²
Serum Chemistry ¹		X			X ⁹	X
Hematology ¹		X			X ⁹	X
Aldosterone and renin ¹		X				
Urinalysis ¹		X			X ⁹	X
Urine HCG		X ⁴				X ⁴
IP Reconciliation						X

- All blood potassium samples are analyzed by i-STAT and by the Central Laboratories on all occasions. Serum clinical chemistry, including S-K, hematology and urinalysis will be measured fasting and before administration of ZS. For diabetic patients all blood potassium samples should be collected prior to insulin administration whenever possible.
- Blood potassium will be measured twice 60 (±15) minutes apart within 1 day of first dose administration on Correction Phase Day 1(Visit 2) and at 4 hours (±15 min) after administration of the first dose of ZS. Potassium will be measured again at 90 minutes (±15 minutes) after taking the second dose for patients with i-STAT potassium ≥6.1 mmol/L or <4.0 mmol/L 4 hours after the first dose. The Central Laboratory serum chemistry, hematology, aldosterone and renin samples will be collected at the same time as the 60 minutes i-STAT screening potassium sample, but will be analysed only in confirmed hyperkalemic subjects.

3. Potassium will be measured predose (0 hour) and 1 hour (± 15 min) after the first dose on Correction Phase Day 2 (Visit 3).
4. U-HCG will be performed exclusively for women of childbearing potential. Samples will be analysed locally, and the data will not need to be collected in the database. Pregnant women are excluded from the study.
5. Visit 3, 4 and 5 (Day 2, 3 and 4 for the Correction Phase) are the same as visit 6 Day 1 in the Maintenance Phase for patients achieving normokalemia in the morning the day of the visit. Patients not achieving normokalemia at Visit 4 will be dosed with ZS 10g TID for an additional 24h and then return to the site for Visit 5.

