6. EOS in Correction Phase only for patients NOT entering the Maintenance Phase, and occurs 7 ± 1 day after the last administration of IP.
7. Baseline parameters should be measured/collected no earlier than 1 day prior to administration of the 1st dose of study drug on Day 1 (Visit 2). Visits 1 and 2 may be combined into a single visit on the same day.
8. A complete physical examination should be performed within 1 day of administration of the first dose of study drug on Correction Phase Day 1, and targeted physical examination will be conducted on EOS.
9. If subject does not qualify for the Maintenance Phase on/before Correction Phase Day 4.
10. AEs will be collected after the patient has signed informed consent, so during the Day 1 (Visit 2), investigator need to check if any AE happened since from inform consent.
11. Blood potassium will be measured upon return to the clinic to determine if the subject is eligible to enter the Maintenance Phase or if the subject should receive an additional 24 hours of dosing.
12. Central laboratory potassium sample collected as part of the serum chemistry panel.

Table 2 Study Plan for the Maintenance Phase

Study Visit (Visit)	6	7	8	9	10	11	12	13	14	15	16	17	18	19	20	21	22	23	EOS	
Maintenance Phase Day⁵ (Day)	1	2	5	12	19	26	54	82	110	138	166	194	222	250	278	306	334	362	One week after last IP⁶	
Targeted physical exam including weight	X			X		X	X	X	X	X	X	X	X	X	X	X	X	X	X	X
SF-36 v2 questionnaire																				X
Access IVRS/TWRS ⁷	X			X		X	X	X	X	X	X	X	X	X	X	X	X	X	X	X
Study drug (IP) dispensation	X			X		X	X	X	X	X	X	X	X	X	X	X	X	X	X	X
Study drug (IP) administration	X			X		X	X	X	X	X	X	X	X	X	X	X	X	X	X	X
ECG	X			X		X	X	X			X			X			X			X
Vital signs	X			X		X	X	X	X	X	X	X	X	X	X	X	X	X	X	X
Concomitant medications	X			X		X	X	X	X	X	X	X	X	X	X	X	X	X	X	X
Adverse events	X			X		X	X	X	X	X	X	X	X	X	X	X	X	X	X	X
Potassium ^{1,2}	X ^{2,3,8}	X ^{2,8}	X ^{2,8}	X ^{2,8}	X ^{2,8}	X ^{2,8}	X ^{2,8}	X ^{2,8}	X ^{2,8}	X ^{2,8}	X ^{2,8}	X ^{2,8}	X ^{2,8}	X ^{2,8}	X ^{2,8}	X ^{2,8}	X ^{2,8}	X ^{2,8}	X ^{2,8}	X ^{2,8}
Serum chemistry ¹	X			X		X	X	X			X			X			X			X
Hematology ¹				X		X	X	X	X	X	X	X	X	X	X	X	X	X	X	X

Table 2 Study Plan for the Maintenance Phase

Study Visit (Visit)	6	7	8	9	10	11	12	13	14	15	16	17	18	19	20	21	22	23	EOS
Maintenance Phase Day ⁵ (Day)	1	2	5	12	19	26	54	82	110	138	166	194	222	250	278	306	334	362	One week after last IP ⁶
Aldosterone and renin										X									X
Urinalysis ¹					X			X		X				X			X		X

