- The site will access the IVRS/IWRS and the system will assign the patient a Correction Phase IP kit.
- The first doses of study IP will be administered as a suspension in water. The patient will be shown/instructed on how to mix and administer the IP, following which the patient is allowed to break the fast.
- 4 hours (± 15 min) after dose administration a potassium sample (i-STAT and Central Laboratory) will be collected.
- Patients with i-STAT potassium levels < 6.1 and ≥ 4.0 mmol/L at the 4 hour (± 15 minutes) post Dose 1 blood draw will be sent home with instructions on how to take the IP. They will be requested to fill out a dosing schedule card indicating when they took the IP. The patient will return to the clinic the following morning of the Correction Phase Day 2 (Visit 3).
- Patients with i-STAT potassium ≥ 6.1 or < 4.0 mmol/L at the 4 hour post Dose 1 blood draw will stay in the clinic and take the second dose of study drug approximately 4-hours after the first dose. They will then remain in the clinic an extra 90 minutes (± 15 minutes) after taking the second dose when another blood

sample for potassium determination (i-STAT and Central Laboratory) will be collected and an ECG will be recorded.

- If the potassium level is > 6.5 mmol/L as determined by the i-STAT at the 90-minute post Dose 2 blood draw, the patient will be discontinued from the study. Patient will return to the clinic 7 (± 1) days later for an EOS visit.
- If the potassium level is ≤ 6.5 mmol/L as determined by i-STAT, and the ECG does not exhibit any of the ECG withdrawal criteria, the patient will be sent home with the 3rd dose of study drug and the dosing card and return to the clinic in the morning of Correction phase Day 2 (Visit 3).

- See section 7.2 regarding how to handle patients with potassium < 3.5 mmol/L.

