4.2.2 Correction Phase Day 2 (Visit 3)

Subjects will arrive at the clinic in the morning after fasting for at least 8 hours prior to potassium sample collection.

- The clinic staff will solicit any adverse events, note any changes in concomitant medications, note if the subject has visited a doctor or emergency room since the last visit, examine the investigational product dosing boxes and sachets and make note of the time the doses were taken and any unused investigational products on the eCRF and source documents.
- Potassium values will be evaluated by i-STAT and the Central Laboratory.
- If the i-STAT potassium value is between 3.0 and 3.4 mmol/L inclusive, the subject should not take a study IP doses that day and return the next day to assess potassium.
 - 1 hour (± 15 min) after first serum potassium measurement a potassium sample (i-STAT and Central Laboratory) will be collected.
- If the i-STAT potassium value is between 3.5 and 5.0 mmol/L, inclusive, the subject will enter the Maintenance Phase and complete the procedures detailed in Section 4.2.5.
- If the i-STAT potassium value is ≥ 5.1 mmol/L, the subject will receive an additional 24 hours of ZS 10 g TID and the following procedures will be performed:
 - The site will access the IVRS/IWRS and provide the 7-digit subject identification number. The system will assign the subject an investigational product kit.
 - An ECG will be performed (Section 5.2.3).
 - The morning dose of ZS will be administered in the clinic as a suspension in water.

- 1 hour (\pm 15 min) after dose administration a potassium sample (i-STAT and Central Laboratory) will be collected.
 - Patients with i-STAT potassium levels ≤ 6.5 and ≥ 3.5 mmol/L at the 1 hour (\pm 15 minutes) post Dose 1 blood draw will be sent home with 2 doses of study drug and instructions on how to take ZS. They will be requested to fill out a dosing schedule card indicating when they took the IP. The patient will return to the clinic the following morning of the Correction Phase Day 3 (Visit 4).
 - If the potassium level is > 6.5 mmol/L as determined by the i-STAT at the 1 hour (\pm 15 minutes) post Dose 1 blood draw, the patient will be discontinued from the study. Patient will return to the clinic 7 (\pm 1) days later for an EOS visit.
- See section 7.2 regarding how to handle patients with potassium < 3.5 mmol/L.

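### The Day 3 Correction Phase rule continues 10 g TID for any i-STAT potassium of 5.1 mmol/L or more, with no stop above 6.5 mmol/L as on Days 1 and 2

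*Protocol*

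**What the plan says.** Section 4.2.3 sorts the Day 3 morning i-STAT value into three bands. A value of 3.0–3.4 mmol/L means no dosing that day, 3.5–5.0 means entry to Maintenance, and for anything higher: "If the i-STAT potassium value is ≥ 5.1 mmol/L, the subject will receive an additional 24 hours of ZS 10 g TID". The morning dose is given in clinic, and then: "Subjects will then be sent home with 2 doses of study drug and instructions on how to take ZS".

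Other places repeat the rule without a ceiling:

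- Synopsis (and Section 1.4), for Day 3: "If the subject is not normokalemic, they will receive an additional 24 hours of ZS 10 g TID treatment (9 total doses").
- Table 1, footnote 5: "Patients not achieving normokalemia at Visit 4 will be dosed with ZS 10g TID for an additional 24h".
- Table 1, footnote 11, where the sample serves only to decide "if the subject is eligible to enter the Maintenance Phase or if the subject should receive an additional 24 hours of dosing".

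Days 1 and 2 each have an explicit upper exit leading to discontinuation. Section 4.2.1: "If the potassium level is > 6.5 mmol/L as determined by the i-STAT at the 90-minute post Dose 2 blood draw". Section 4.2.2: "If the potassium level is > 6.5 mmol/L as determined by the i-STAT at the 1 hour" post-dose draw.

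The general criterion is in Section 3.9: "Patient develops potassium values which meet the IP discontinuation criteria described in" Table 6, subject to a confirmatory i-STAT value 10 ± 2 minutes later.

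**The concern.** Days 1 and 2 treat a post-dose potassium above 6.5 mmol/L as a reason to stop. On Day 3, after up to six 10 g doses, Section 4.2.3 taken literally tells the site to dose a patient with such a value and send the patient home.

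What is at stake is the patient's access to other treatment. Section 7.7 bars alternative hyperkalemia therapy until the investigational product is stopped or completed. If no rule clearly stops dosing on Day 3, access depends on the investigator's own judgement or on how the site reads Table 6. Sections 1.4 and the synopsis promise stopping rules for significant hyperkalemia, and this visit does not state one.

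**Working it through.** This is a comparison of rules. No sample size, power or error rate is involved, and the plan states no figure to reproduce.

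**1. The exits side by side.** Sample counts are from Table 4.

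| Step | Values used | Written outcome above 6.5 mmol/L | Potassium samples | Of these, post-dose |
|---|---|---|---|---|
| Day 1 (4.2.1) | 4 h after Dose 1; also 90 min after Dose 2 if the 4 h value is ≥6.1 or <4.0 | Discontinue on the 90-minute value | 3–4 | 1–2 |
| Day 2 (4.2.2) | Morning; 1 h after the morning dose | Discontinue on the 1 h value | 2 | 1 |
| Day 3 (4.2.3) | Morning only | None stated; falls in the ≥5.1 band, so dose and discharge | 1 | 0 |
| Day 4 (4.2.4) | Morning | Discontinue (any value ≥5.1) | 1 | no Correction Phase dose |
| Maintenance (Table 6) | Visit value | Discontinue, in all four dose rows | – | – |

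**2. A test value of 6.6 mmol/L.** At the Day 2 1-hour draw, the patient is discontinued. On the Day 3 morning draw, the patient is dosed and discharged.

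**3. What the two earlier days guarantee.** On Day 1 a patient goes home either with a 4 h value below 6.1 or with a 90-minute value of at most 6.5. On Day 2 discharge with further doses requires a 1 h value of 3.5–6.5. So on both days the last value before leaving with study drug is at most 6.5. On Day 3 the last value before leaving is the morning one, and it has no bound.

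**4. Exposure after the last check.** From the Day 3 sample to the Day 4 sample: 3 doses × 10 g = 30 g, one in clinic and two at home, with 0 scheduled samples. After the Day 2 1-hour sample: 2 × 10 g = 20 g before the next scheduled sample.

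**5. Does another section supply the stop?**

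- Section 4.2.3 refers to Section 7.2 only for potassium below 3.5.
- The Correction Phase text of Section 7.2 gives a low stop (below 3.0) and no high stop.
- Section 3.9 refers to Table 6, which Section 7.2 introduces under Maintenance dosing. Its rows run from 5 g QOD or 2.5 g QD to 15 g QD, with none for 10 g TID.
- The peaked T-wave instruction in Section 3.9 returns the decision to the Section 3.9 criteria, and so to the same table.

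**6. Could Table 6 be the Correction Phase rule?** Applied literally, it conflicts with that phase in three places:

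- Day 1: a 4 h value of 6.1 or more, which includes values above 6.5, leads to the second dose. Table 6 would stop dosing above 6.5.
- Day 2: any pre-dose value of 5.1 or more is dosed. Table 6 would stop those above 6.5.
- A value of 3.0–3.4 is a one-day hold in the Correction Phase. Table 6 reduces the dose or discontinues.

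If Table 6 is nonetheless meant for Day 3, it conflicts with the mandatory dosing instruction in Section 4.2.3. Either reading needs a change to the text.

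**7. How many patients?** Those dosed on Day 2 had a 1 h value of at most 6.5. A Day 3 value above 6.5 therefore needs a rise on treatment, or a rebound after a Day 2 hold for 3.0–3.4. The protocol gives no data from which to estimate this.

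**The case against.** The best case for the text as it stands is that a general rule already covers Day 3. The synopsis and Section 1.4, in a paragraph written for all study phases, base stopping rules on i-STAT values under Section 7.2. Section 3.9 names no phase in its potassium criterion and gives discontinuation procedures for both phases. Table 6 stops dosing above 6.5 in every row, so the criterion does not depend on the current dose. This makes an inferred stop reasonable. It does not make it explicit: Section 3.9 says only that patients may be discontinued, while Section 4.2.3 says they will be dosed, and the conflicts in step 6 show that Table 6 cannot govern the whole Correction Phase.

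Three further points have some force:

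- **Figure 4**, the Correction Phase flow chart, is not visible in the copy reviewed and may hold the stop. That stands as a limit on the finding. If the figure has the stop, the visit text still needs to match it.
- **The comparison is not like for like.** The earlier stops use post-dose values, and the Day 2 pre-dose band is equally open. This is true, but on Day 2 a post-dose check with a stop follows before discharge. Day 3 has only the morning value, so a stop there must use it.
- **Other safeguards remain.** A Day 3 ECG is done before dosing, the ECG and arrhythmia stops apply, and the investigator may discontinue a patient judged to be at risk. These reduce the hazard without giving a potassium threshold.

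It is also fair that no primary endpoint or sample-size conclusion changes; the primary objective concerns Maintenance Phase safety.

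**Conclusion.** The point holds. Section 4.2.3 sets no upper limit on continued 10 g TID dosing on Day 3, and the text gives no explicit stop above 6.5 mmol/L for that visit, although Days 1, 2 and 4 and every Table 6 row have a high-potassium exit. The consequence is up to 30 g of further dosing with no scheduled potassium until the next morning, in a patient whose value would have ended treatment at the post-dose check the day before.

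The number affected should be small and cannot be derived from the protocol. The conclusion is about the visible text: it assumes nothing about Figure 4, and it allows that a site could infer the stop from Section 3.9. It should be fixed, because the possible harm is serious and the correction is easy. Confidence is medium, mainly because of the unseen figure.

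**What to change.** - **Section 4.2.3:** limit the continue-dosing branch to 5.1–6.5 mmol/L. Add that a Day 3 i-STAT value above 6.5, confirmed at 10 ± 2 minutes, leads to discontinuation, appropriate treatment, the Visit 5 procedures that Section 3.9 already requires, and an EOS visit 7 (±1) days after the last dose.
- **Section 3.9:** list the Correction Phase criteria above 6.5 separately from Table 6: Day 1 at 90 minutes after Dose 2, Day 2 at 1 hour post-dose, Day 3 on the morning value.
- **Alignment:** bring Table 1 footnotes 5 and 11, the synopsis, Section 1.4 and Figure 4 into agreement.
- **Limit of the change:** do not extend the stop to the Day 1 qualifying or 4-hour samples or the Day 2 pre-dose sample. That would create an entry ceiling and override the dose-then-reassess design of those days.

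The cost is protocol wording. The Day 3 value is already measured, no visit is added, and the only new sample is the 10-minute confirmation. The downside is that a few patients above 6.5 on Day 3 leave the Correction Phase one day earlier.
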